## IV. Eligibility Criteria

### 1. Inclusion criteria

- Age from 18–65 years.
- body mass index (BMI) ranged between 20 and 40 kg/m^2
- ASA I, II patients undergoing **open thoracic surgery through a posterolateral thoracotomy**

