GA will be induced for both groups using IV fentanyl 2 µg/kg and propofol 2 mg/kg. Tracheal intubation will be facilitated by Atracurium 0.5 mg/kg and will be done either by a left-sided double-lumen endobronchial tube (**Mallinckrodt's 35 to 41 F according to patient size**), or single lumen ETT and a fiberoptic bronchoscope will be used to ensure the correct position of the tube. The tidal volume will be adjusted to be 6–8 ml/kg, and the respiratory rate will be adjusted to keep the end-tidal CO2 between 30 and 40 mmHg.(2)

Anesthesia will be maintained with inhaled Isoflurane with MAC 1-1.5 in oxygen-enriched air (Fio2 will be adjusted to keep peripheral O2 saturation ≥90%) and top-up doses of Atracurium (0.1 mg/kg) IV will be administered as required. Ringer acetate will be infused to replace their fluid deficit, maintenance, and losses. (2)0

Additional bolus doses of fentanyl one  $\mu\text{g}/\text{kg}$  IV will be given if the mean arterial blood pressure (MAP) or heart rate (HR) rises above 20% of baseline levels after exclusion of all causes leads to an increase of both HR and MAP as awareness and fading of neuromuscular blockade.

One reading of MAP and HR will be taken before induction of GA to be defined as a baseline reading and then will be recorded immediately before surgical incision and at 30 min intervals intraoperatively. Hypotension will be treated with 100 ml 0.9% normal saline bolus and 5 mg ephedrine IV in incremental doses to maintain MAP above 70 mmHg. Bradycardia (HR <60) will be treated with 0.1 mg/Kg atropine IV.(2)

At the end of the surgery, the residual neuromuscular blockade will be reversed using 0.07 mg/kg Prostigmin IV, and extubation will be performed after complete recovery of the airway reflexes.

Then, patients will be transferred to the post-operative care unit (PACU) and will be observed for two hours. Following that, the patients will be transferred to a ward and given 1 g of acetaminophen IV every 8 hours, ketorolac tromethamine 30mg IM/12h as 2 components of multimodal anesthesia regimen for postoperative pain control. (10)

VAS (at rest and cough), MAP, and HR will be noted immediately on arrival to PACU (0 h) and at 2, 4, 6, 12,18, and 24 h postoperatively. Rescue analgesia will be provided in the form of IV morphine 3 mg boluses if VAS >3. The time to first request rescue analgesia and the total morphine administered during the first 24-hour postoperative will be recorded.

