Patient satisfaction (satisfied or not satisfied) will be recorded 24 hours postoperative. Adverse events will be reported (PONV, hypotension, bradycardia, excessive sedation, and hematoma).

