### **2. Secondary outcome(s).**

- **Pain score according to VAS score at 30min, 2h, 4h, 8h, 12h, 24h postoperative.**
- **Heart rate and MAP at 0 , 15min, 30min, 45min, 60min, 90min, 120min, then every 1h intraoperative.**
- **First request of analgesia postoperative.**
- **Opioid requirements intraoperatively.**
- **Incidence of complications as hypotension, bradycardia, postoperative nausea, vomiting (PONV) and pruritis.**

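### The printed atropine dose for bradycardia, 0.1 mg/kg IV with no increment or maximum stated, comes to 7 mg at 70 kg and should be verified before any patient is treated

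*Combined protocol and SAP*

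**What the plan says.** The rule stands in the combined protocol and SAP, section V (Study Procedures), Study Protocol, in the paragraph on intraoperative haemodynamics: "Bradycardia (HR <60) will be treated with 0.1 mg/Kg atropine IV". It ends with a citation of reference 2. The only condition is the heart-rate threshold. No increment, reassessment step or maximum is stated, and neither symptoms nor low blood pressure are required. Atropine is mentioned nowhere else in the document.

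The sentence just before it handles hypotension differently. After a saline bolus, it gives "5 mg ephedrine IV in incremental doses to maintain MAP above 70 mmHg". That rule has a step size and a target, though no maximum.

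The people exposed to the rule are adults ("Age from 18–65 years") with "body mass index (BMI) ranged between 20 and 40" kg/m². The eligibility criteria state no weight or height limits and no minimum baseline heart rate. Bradycardia is expected as an event to record: it is named in the adverse-event list at the end of Study Protocol and again among the secondary outcomes ("Incidence of complications as hypotension, bradycardia, postoperative nausea, vomiting (PONV) and pruritis").

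**The concern.** A per-kilogram dose in an adult population is multiplied by a large number, so a small error in the coefficient becomes milligrams of drug. Here the coefficient gives several milligrams of atropine, and the trigger can be met by a heart rate only just below 60. The threshold is absolute rather than relative to the patient's own baseline, so a patient with a low resting rate could meet it after a small fall. A clinician who follows the line literally finds nothing in it that says to give less and look again.

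What is at stake is the safety of the patients who meet the trigger, in either arm. The rule is the same for both groups.

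**Working it through.** The plan derives no total dose, so there is no figure of its own to reproduce. The check is direct multiplication.

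**Inputs from the document**
- Dose coefficient: 0.1 mg/kg (section V, Study Protocol).
- BMI limits: 20 and 40 kg/m² (section IV, Inclusion criteria).

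**Inputs assumed here**
- An example weight of 70 kg.
- Heights of 1.60 to 1.80 m, with 1.50 to 1.90 m as a wider range.
- A usual adult total of 1 to 3 mg atropine. This is general practice and is not in the documents.

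**Formulas:** weight = BMI × height²; dose = 0.1 × weight.

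| Case | Weight (kg) | Dose as printed (mg) | Excess over 3 mg (mg) |
|---|---|---|---|
| BMI 20, 1.60 m | 20 × 1.60² = 51.2 | 5.12 | 2.12 |
| Example | 70 | 7.0 | 4.0 |
| BMI 40, 1.80 m | 40 × 1.80² = 129.6 | 12.96 | 9.96 |

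With the wider heights, the ends are 20 × 1.50² = 45.0 kg, giving 4.5 mg, and 40 × 1.90² = 144.4 kg, giving 14.4 mg.

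**How far the result depends on the benchmark.** The printed dose passes 3 mg at 3 / 0.1 = 30 kg. At the lowest eligible BMI, 30 kg is a height of √(30/20) = 1.22 m, so in practice every eligible adult is above it. A benchmark of 4 mg is passed at 40 kg (1.41 m at BMI 20), and one of 5 mg at 50 kg (1.58 m at BMI 20). Over heights of 1.60 to 1.80 m the lightest patient receives 5.12 mg, so any assumed total below 5.1 mg is exceeded for everyone in the range. Over 1.50 to 1.90 m the same holds for any total below 4.5 mg.

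**Illustration only.** If the coefficient were one decimal place too large, 0.01 mg/kg would give 0.7 mg at 70 kg, and 0.51 to 1.30 mg over 51.2 to 129.6 kg. The documents do not establish that this is the intended figure.

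**The case against.** The strongest reply is that nothing in the documents says what the right dose is. The comparison rests on an outside benchmark, and the sensitivity check does not remove that dependence: a reader must still accept from elsewhere that a usual adult total lies below about 5 mg. This stands. It is why the benchmark is declared as an assumption and the first action is to verify.

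Second, the absence of a maximum is the general style of this section. Fentanyl, propofol, atracurium and the reversal dose ("0.07 mg/kg Prostigmin IV") are all per-kilogram doses without a cap, and the ephedrine rule has none either. This stands too. A reader might infer that the missing cap singles atropine out; it does not. What needs attention is the figure of 0.1, and the stepwise wording is an improvement that comes second.

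Third, a reader might infer that the protocol orders one single bolus. It does not use that word. One per-kilogram figure with no increments reads most naturally that way, but this remains a reading.

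Fourth, the number may be an artefact of reading the PDF, or may come from reference 2. The evidence on text reading is mixed. The reversal dose in the same section kept two decimals, whereas the sample size section prints its mean and SD with equals signs where decimal points would be expected. The source is not available, so neither explanation can be confirmed or excluded, and it would be wrong to state that a decimal point was misplaced.

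Fifth, the documents give no expected frequency of heart rates below 60, and the 13 mg end requires BMI 40 at 1.80 m. Both are true. Listing bradycardia as an outcome shows that it is anticipated, not how often it will occur. The 70 kg example is enough for the point.

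That anaesthetists would not follow the line literally may well be so, but a written drug instruction should not rely on being disregarded.

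**Conclusion.** The point holds as a patient-safety concern about one printed figure. For a patient who meets the trigger, the rule as written gives 7 mg at 70 kg and 5.1 to 13.0 mg across the eligible BMI range at heights of 1.60 to 1.80 m. That is above the upper end of an assumed 1 to 3 mg adult total by 2.1 to 10.0 mg, and by 4.0 mg at 70 kg. The conclusion rests on the assumed heights and on a usual adult total below 5.1 mg; it does not need 3 mg to be exact.

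Confidence is medium, because the origin of the figure cannot be seen. A reader might go further and infer that the rule threatens the morphine comparison. The documents give no support for that: the rule applies equally to both arms, and no effect on the primary outcome, bias or power is claimed.

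**What to change.** **Required, before any patient is treated.** Check 0.1 mg/kg against the original protocol page, cited source (2) and the product label, and correct it if it is wrong. If the original page shows a different figure and that figure agrees with the source and the label, the dose question closes there.

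**Recommended in the same amendment.** Write the rule in steps, as the adjacent ephedrine rule does for MAP. For example: for a heart rate below 60, give atropine [X] mg IV, reassess heart rate after each dose, stop once it is 60 or above, and do not exceed a total of [Y] mg. The maximum is an addition, since the ephedrine rule has none. X and Y are for the anaesthesia lead and pharmacy to set; no dose is proposed here.

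**Cost.** A pharmacy check and a one-line amendment. Sample size, schedule and analysis are unaffected.

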### Measured Parameters:

- Hemodynamics including MAP and HR throughout the surgery
- VAS (at rest and cough), MAP, and HR will be noted immediately on arrival to ICU (0 h) and at 2, 4, 6, 12,18, and 24 h postoperatively figure (1).

[figure not shown]

Figure1:Visual analog score (8)

- **Post-operative Total amount of morphine consumption in the first 24-hour.**
- Incidence of complications, such as nerve injury, hematoma formation, and severe hypotension will be noted.

## **VI. Study outcomes**

### **1. Primary outcome**

- **Total amount of morphine consumption in the first 24-hour postoperative in the two groups.**

### **2. Secondary outcome(s).**

- **Pain score according to VAS score at 30min, 2h, 4h, 8h, 12h, 24h postoperative.**
- **Heart rate and MAP at 0 , 15min, 30min, 45min, 60min, 90min, 120min, then every 1h intraoperative.**
- **First request of analgesia postoperative.**
- **Opioid requirements intraoperatively.**
- **Incidence of complications as hypotension, bradycardia, postoperative nausea, vomiting (PONV) and pruritis.**

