### 1. Study Protocol

Preoperative assessment of all patients comprised of history taking, clinical examination, laboratory testing (complete blood count, kidney function tests, liver function tests, prothrombin time, and partial thromboplastin time), electrocardiogram, and chest X-ray. The study protocol will be explained to the patients, and their consent will be obtained. All patients will be made familiar with the use of the pain score; visual analog scale score (VAS) identifying 0 as no pain and ten as the worst possible pain.

The patients will be continuously monitored in the holding room for **heart rate**, blood pressure, and oxygen saturation (baseline values). An intravenous (IV) 18-

gauge cannula will be inserted. Midazolam **2mg boluses** IV will be administered for each patient. Patients will receive US-guided ESPB and US-guided ESPB + US-guided Retrolaminar plain block before induction of GA.

US-guided ESPB Blocks will be performed with a US machine (Philips HD 11xe) equipped with an HFL38X high-frequency linear transducer (13–16 MHz). With patients in a sitting position, the transducer will be positioned longitudinally 3 cm lateral to the T5 spinous process. The trapezius, rhomboid major, and erector spinal muscles will be revealed superficial to the shadow of the hyperechoic transverse process. Then, 3 ml lidocaine 2% will be used to anesthetize the skin. Using a 20-gauge block needle **inserted** in-plane in a cephalad-to-caudad orientation to position the tip into the fascial plane on the deep (anterior) side of the erector spinae muscle, 20 ml bupivacaine 0.25% will be injected. The needle tip's placement was confirmed by observable fluid spread lifting the erector spinae muscle away from the transverse process's bony shadow. (2)

For the retrolaminar block, an in-plane technique under ultrasound guidance will be used to advance the needle towards the posterior surface of the T5 lamina in a cephalic to caudal direction until contact with the lamina will be made. After confirming contact, the correct spread will be verified by injecting 1.0–2.0 ml of saline to create a plane of hypoechoic space on the posterior surface of the T5 lamina,(7) and 10 ml bupivacaine 0.25% will be injected.

**The block success will be assessed by a blind observer unrelated to data collection. The presence of the cold sensation in T1-T8 dermatomes in the blocked side after 30 minutes indicated a failed block, and the patient will be excluded . (9)**

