## Sample size

### Statistical Analysis

#### 1) Sample size

Power analysis was performed using G power software on the level of **total amount of morphine consumption in the first 24-hour postoperative** as it is the primary outcome in the current study using a student t-test.

A previous study showed that total amount of morphine consumption in the first 24-hour postoperative , mean(SD) **after ESPB was 8=52(4=29) mg. (9)**

Based on assumption that a 50% difference between groups is a clinically significant difference and for a power **of 0.95 and alpha error of 0.05.**

A minimum of **16** patients was calculated for each group. The sample size will be increased to **18** for each group to compensate for possible dropouts.

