#### 2) Statistical analysis

- Microsoft excel 2013 will be used for data entry and the statistical package for social science (SPSS version 24) will be used for data analysis.
- Simple descriptive statistics (arithmetic mean and standard deviation) will be used for the summary of normal quantitative data (median and interquartile range) for a summary of abnormal quantitative data and frequencies will be used for qualitative data.
- Bivariate relationship will be displayed in cross-tabulations and a Comparison of proportions will be performed using the chi-square and Fisher's exact tests where appropriate.
- **T-test** and post-hook tests will be used to compare normally distributed quantitative data and Kruskal-Wallis for skewed data.
- P value will be calculated to assess statistical significance, a value less than 0.05 will be considered statistically significant.

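### Heart rate and MAP have recorded baselines, but the analysis plan never adjusts for them: the unadjusted comparison is valid, yet may give up precision and leaves chance baseline gaps uncorrected

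*Combined protocol and SAP*

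**What the plan says.** Section VI, Secondary outcome(s), lists "Heart rate and MAP at 0 , 15min, 30min, 45min, 60min, 90min, 120min, then every 1h intraoperative". These are values at set times; no change from baseline or adjusted measure is named.

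Two sets of readings are called baseline, both under Study Protocol in section V:

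- In the holding room, patients are monitored continuously for heart rate, "blood pressure, and oxygen saturation (baseline values"). No single reading is designated, and MAP is not named there.
- Later in the same section: "One reading of MAP and HR will be taken before induction of GA to be defined as a baseline reading". The block also precedes induction: "Patients will receive US-guided ESPB and US-guided ESPB + US-guided Retrolaminar plain block before induction of GA". The text does not say whether this reading comes before or after the block.

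The one stated use of baseline is as a trigger for extra intraoperative fentanyl, when MAP or heart rate "rises above 20% of baseline levels".

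For quantitative data, the Statistical analysis section says only that the t-test "and post-hook tests will be used to compare normally distributed quantitative data and Kruskal-Wallis for skewed data". It mentions no covariate, change score or repeated-measures model, and has no sentence specific to heart rate or MAP.

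**The concern.** A patient's resting heart rate and MAP before treatment may predict the values seen later. If so, ignoring them leaves between-patient variation in the comparison that a covariate would remove. In arms of 15 to 18, the baseline means can also differ noticeably by chance. Part of that difference then sits in the observed difference between arms, where it can resemble a block effect or mask one.

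At stake are the precision and readability of two named secondary outcomes. There is also an open analytic choice. With two candidate baselines, an undefined time 0 and no stated model, the choice between raw, change-score and adjusted analyses could be made after the data are seen.

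**Working it through.** **Plan's own figure.** The documents give no SD, effect, power or correlation for heart rate or MAP, so there is none to reproduce. The sample size section's minimum of 16 per group rests on 24-hour morphine, and I use it only as the number of patients. The plan also gives 15 per group (Randomization) and 18 per group (with dropouts), so those are shown too.

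**Assumptions, not from the documents.** Correlation r between baseline and a later reading, from 0 to 0.7; equal SD in both arms; for power only, a true difference of 0.75 SD, two-sided alpha 0.05, at a single time point.

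**Step 1: size of a chance baseline gap.** In patient SD units, the SD of the gap is √(2/n). At n = 16 this is √(2/16) = 0.354, giving a 95% range of ±1.96 × 0.354 = ±0.69. The probability of a gap above 0.5 SD is 2 × [1 − Φ(0.5/0.354)] = 0.157. It is 0.171 at 15 per arm and 0.134 at 18.

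**Step 2: how much carries through.** The expected shift in the later raw comparison is r × gap. For a 0.5 SD gap it is 0.15, 0.25 and 0.35 SD at r = 0.3, 0.5 and 0.7. As an illustration, if the SD of MAP were 12 mmHg, the gap would be 0.5 × 12 = 6 mmHg and the shift at r = 0.5 would be 3 mmHg.

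**Step 3: precision after adjustment.** The variance of the adjusted estimate relative to raw is (1 − r²) × (1 + 1/(N − 4)), where N is total patients and the second factor is the price of estimating the slope. At N = 32 that factor is 1 + 1/28 = 1.036.

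**Step 4: power at 0.75 SD, 16 per arm.** The raw noncentrality is 0.75/0.354 = 2.12 on 30 degrees of freedom, giving power of about 0.54. For the adjusted test, divide 2.12 by the standard-error ratio and use 29 degrees of freedom.

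| r | Variance ratio | Standard-error ratio | Power, adjusted |
|---|---|---|---|
| 0 | 1.04 | 1.02 | 0.52 |
| 0.2 | 0.99 | 1.00 | 0.54 |
| 0.3 | 0.94 | 0.97 | 0.56 |
| 0.5 | 0.78 | 0.88 | 0.64 |
| 0.7 | 0.53 | 0.73 | about 0.80 |

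**Step 5: break-even.** Setting the variance ratio to 1 gives r = √(1/(N − 3)) = √(1/29) = 0.19 at 16 per arm. It is 0.19 at 15 and 0.17 at 18.

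**Step 6: change scores.** A change score has variance ratio 2(1 − r): 1.4 at r = 0.3, 1.0 at 0.5 and 0.6 at 0.7. It is worse than raw below r = 0.5, so it is not a safe substitute for covariate adjustment.

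**The case against.** The strongest reply is that the planned test is not wrong. Randomisation makes the raw difference unbiased on average, and its standard error already includes chance baseline variation, so the 5% level holds over all randomisations. A reader might infer from the baseline gaps that the planned analysis is biased or has an inflated false-positive rate. The documents do not support that. This objection stands in full. What adjustment adds is a correction for the gap in the one trial actually run, and a narrower interval when r is large enough.

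A reader might also infer that the whole baseline gap passes into the result. Only r times the gap does.

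Nor is the gain guaranteed. Intraoperative values are actively managed against limits stated in the protocol, which could plausibly weaken their correlation with awake holding-room values. If r is 0.2, adjustment gains almost nothing. To call it free precision would go beyond the documents, which give no r. This limits the claim but does not remove it: the loss at r = 0 is about 4% of variance, against a gain of about 22% at r = 0.5.

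Finally, the analysis text is generic, so the use of raw values is an inference from the outcome list and the only methods named. That is fair. But no other text governs these outcomes, so any intended adjustment still has to be written down.

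**Conclusion.** The point holds as a modest improvement. The plan records baseline heart rate and blood pressure but does not use them to analyse two secondary outcomes. The unadjusted comparison remains valid. At 16 per arm it leaves uncorrected a baseline gap above 0.5 SD in about 16% of randomisations. Adjustment would change the variance of the estimate by between +4% (r = 0) and −47% (r = 0.7), with a net gain only above r of about 0.19. Correlation, effect size and equal SDs are assumptions; the number per arm is the plan's own.

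The choice of covariate matters as much as the decision to adjust. The reading the protocol formally defines as baseline may follow the block, and adjusting for a value the block has already altered could remove part of its effect. The holding-room text does not yet designate one MAP reading.

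The primary conclusion on 24-hour morphine is not affected. No stated hypothesis or sample-size figure rests on heart rate or MAP.

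**What to change.** In the Statistical analysis section:

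- State that post-block heart rate and MAP are compared by a baseline-adjusted model. Either a mixed model with arm, time, arm-by-time and baseline, or analysis of covariance at one named time or on the intraoperative mean, would serve. Naming one avoids a separate test at every listed time.
- Report adjusted mean differences with 95% intervals in place of raw t-tests.
- Designate as covariate one holding-room reading of heart rate and MAP taken before the block.

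In Study Protocol and Secondary outcome(s):

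- Reconcile that covariate with the pre-induction baseline reading, and say whether the latter precedes the block.
- Say whether time 0 in the outcome list is the covariate reading. If it is, it is not an outcome.
- Reconcile the two recording schedules. Study Protocol has readings just before incision and then every 30 minutes, while the outcome list includes 15 and 45 minutes.

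The cost is a few sentences, one designated pre-block reading and one baseline term (one degree of freedom), with a variance penalty of about 4% if baseline proves uncorrelated with later values. No extra patients are needed.
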